#### 5 SELECTION AND WITHDRAWAL OF SUBJECTS

#### 5.1 Inclusion Criteria

Approximately 300 subjects with known history of due to multiple sclerosis, treated with a stable dose of are to be enrolled. Subjects are required to consent to participate in the study. They will be informed that their primary medical practitioner and physiotherapist may be contacted to inform them of the study and its conditions. Subjects must fulfill inclusion/exclusion criteria as listed below.

- 1. Men and women age 18 years and older
- 2. Women of child bearing potential practicing an acceptable method of birth control for the duration of the study as judged by the investigator(s) [such as condoms, foams, jellies, diaphragm, intrauterine device (IUD), oral or long acting injected contraceptives, bilateral tubal ligation or vasectomized partner] for at least 3 months prior to study entry OR postmenopausal for at least 1 year OR surgically sterile (bilateral oophorectomy or hysterectomy)

3.	If female, negative pregnancy test	
4.		

Confidential Page 34 of 67

- Has an ECG that is not clinically significantly, abnormal and a blood pressure <160/95 mmHg
  (systolic/diastolic) at screening, measured in the sitting position after approximately 5 minutes
  of quiet rest

- 8. If the subject has a history of or presence of clinically significant liver disease, diabetes mellitus, hypertension or heart disease, the subject must be on a stable treatment regimen for a minimum of 3 months prior to Screening Visit
- 9. Able and willing to comply with the protocol, including availability for all scheduled clinic visits
- 10. Willingness and giving of written informed consent

[figure not shown]
5.2	Sub	iect	Exclusion	Criteria

1.

6.

- Concomitant neurologic conditions causing spasticity (e.g., stroke, cerebral palsy, traumatic brain injury) or rigidity (e.g., Parkinson's disease, contractures that confound assessment of spasticity)
   Advanced arthritis or any other cause of clinically significant limitation of passive range of motion around any of the injure being assessed in this study.
- motion around any of the joints being assessed in this study

  Any medical condition, including psychiatric disease or epilepsy, which would interfere with
- 5. Any medical condition, including psychiatric disease or epilepsy, which would interfere with the interpretation of the study results, the conduct of the study, or the safety of the subject

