#### 10.4.1 Demographic and Other Baseline Characteristics

Descriptive summaries of the Safety Population will be prepared for the demographic and baseline (Screening) characteristics listed below. Categorical variables will be described with counts and percentages, ordinal variables with medians and quartiles, and interval variables with mean and 95% confidence interval (CI).

Descriptive comparisons will be made using the Pearson's chi-square test for categorical variables, Mann-Whitney U-test for ordinal variables, and Student's two-sample t-test for interval variables.

- Age (years)
- Gender
- Race/ethnicity
- Renal function (as estimated by calculated creatinine clearance)
- •
- •
- •

Confidential Page 54 of 67

[figure not shown]
Medical history at Visit 1 (prior conditions and present conditions) will be tabulated by body system, both with a summary of incidence by diagnosis and the numbers and proportions with any abnormality. A by subject listing will be created.

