#### • Missing AE Stop Dates

If the stop date is completely missing and the event is not ongoing (i.e., an outcome is indicated), the stop day will not be estimated.

If only the day of resolution is unknown, the day will be assumed to the last of the month (e.g. ??-JAN-2011 will be treated as 31-JAN-2011)

If the stop date is completely missing and the event is ongoing, the event will be noted as "Ongoing" in the stop date column in the AE listings.

The incidence of TEAEs and serious adverse events (SAEs) will be summarized

An overall summary of TEAEs will include:

- o Incidence of subjects with one or more TEAE
- o Incidence of TEAEs by highest relationship
- o Incidence of TEAEs by highest severity
- o Incidence of TEAEs by action taken
- o Incidence of TEAEs by outcome
- o Incidence of treatment-emergent SAEs

The incidence of TEAEs will be presented by system organ classification and preferred terms, by highest relationship, by treatment-related status (possibly, probably, certainly), by highest severity, by descending order of frequency of preferred terms, by dose at earliest onset for all possible dose groups, and by discontinuation status.

In addition, separate summaries of TEAEs will be prepared with subjects categorized by sex, age (below 65 years of age and 65 years of age and older), race, and renal impairment category (see Section 6.1.2).

The effects of concomitant medications and/or medical conditions present at screening will also be explored. Should any medications be used by or conditions be present in 20% or more of the subjects overall, subjects will be categorized accordingly and the incidence of TEAEs in each part summarized. Additional drugs or diagnoses of interest may be identified during the blinded data review.

The incidence of treatment-emergent serious adverse events (SAEs) will be presented by system organ classification and preferred terms, by treatment-related status (possibly, probably, certainly), and for those that are fatal.

Adverse events will be listed for all subjects, including verbatim and coded terms.

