## Urinalysis:

- Dipstick for pH, specific gravity
- Microscopic examination of the sediment
- Urine pregnancy test (for women) to be performed at Screening, Visit 4 (Week 6), and Visit 7 (Week 14)

Scheduled laboratory testing will be performed at a central laboratory using sex- and age-appropriate normal ranges. Laboratory tests may also be repeated between scheduled visits at the discretion of the Investigator. In addition, repeat testing should be performed at the end of the study to follow any clinically significant abnormality to resolution/stabilization.

Clinical laboratory testing (hematology, chemistry, and urinalysis) results at each visit (Screening and Visit 7) and its change from Screening (for all continuous clinical laboratory parameters) will be summarized using descriptive statistics (n, mean, 95% confidence interval, standard deviation, minimum, median, and maximum) using Conventional units. Where applicable (e.g., red blood cell indices), results will be presented separately for men and women. For the summary of change statistics, the Baseline mean and standard deviation will be provided for the subset of subjects with available data for the change summary. Summaries will be based on values obtained from the central laboratory only and appropriate visit windows for categorizing results will be established prior to database lock and unblinding.

When more than one laboratory value is available within a given visit window, the latest value will be used for tabulation purposes.

Criteria for possibly significant changes have been established for selected parameters, tabulated below. The numbers and percentage of subjects meeting these criteria will be summarized.

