#### **PCS Blood Chemistry Parameters**

Parameter	PCS values	
	S.I. Units	Conventional Units
Sodium	≤ 115 or ≥ 155 mmol/L	≤ 115 or ≥ 155 mEq/L
Potassium	≤ 3.0 or ≥ 5.8 mmol/L	$\leq$ 3.0 or $\geq$ 5.8 mEq/L
Glucose (random)	≤ 2.775 or ≥ 9.99 mmol/L	≤ 50 or ≥ 180 mg/dL
BUN	≥ 30 mg/dL	> 30 mg/dL
Creatinine	≥ 176.8 µmol/L	≥ 2.0 mg/dL
Calcium, plasma	≤ 1.75 or ≥ 3.875 mmol/L	≤ 7 or ≥ 15.5 mg/dL
ALT / SGPT	≥ 3 × ULN	≥ 3 × ULN
AST / SGOT	≥ 3 × ULN	≥ 3 × ULN
Alkaline phosphatase (ALK-P)	≥ 3 ×ULN	≥ 3 × ULN
Total bilirubin	≥ 34.2 µmol/L	≥ 2.0 mg/dL
Total protein	≤ 45 or ≥ 90 g/L	$\leq 4.5 \text{ or } \geq 9.0 \text{ g/dL}$
Albumin	≤ 25 or ≥ 65 g/L	$\leq 2.5 \text{ or } \geq 6.5 \text{ g/dL}$
Creatinine clearance	< 70 mL/min	< 70 mL/min

S.I. = International System of Units; ULN = upper limit of the [normal] reference range Medium = serum, unless otherwise noted

Clinical laboratory results will be listed for all subjects, inclusive of flags for whether or not the value is outside laboratory normal range, considered significant by the Investigator, or meet the pre-specified criteria for being possibly clinically significant. Normal ranges will be noted in the listing. Values outside laboratory normal ranges as well as those considered clinically significant by the Investigator will be flagged as L (low) and H (high).

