#### PCS Values for Vital Signs

Parameter	PCS Criteria
Systolic Blood Pressure	≤ 90 mmHg and a decrease of ≥ 30 mmHg from baseline* or ≥ 180 mmHg and an increase of ≥ 40 mmHg from baseline
Diastolic Blood Pressure	≤ 55 mmHg and a decrease of ≥ 20 mmHg from baseline or ≥ 90 mmHg and an increase of ≥ 30 mmHg from baseline
Pulse	≤ 50 bpm and a decrease of ≥ 30 bpm from baseline or ≥ 120 bpm and an increase of ≥ 30 bpm from baseline

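### The laboratory PCS limits are described as changes but ignore Screening status, so conditions present at entry can be counted as if they arose on treatment

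*SAP*

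**What the plan says.** SAP 6.3.2 presents the laboratory criteria with "Criteria for possibly significant changes have been established for selected parameters, tabulated below", and then says "The numbers and percentage of subjects meeting these criteria will be summarized". Protocol 10.4.5.4 also describes them as changes. The limits in the two SAP tables are levels. For random glucose, for example, the limit is "≤ 50 or ≥ 180 mg/dL"; for ALT, AST and alkaline phosphatase it is a multiple of ULN.

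The vital-sign table in SAP 6.3.3 is built differently. Its lower systolic criterion reads "≤ 90 mmHg and a decrease of ≥ 30 mmHg from baseline", so a level and a change are both needed.

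Protocol 5.1, criterion 8, begins "If the subject has a history of or presence of clinically significant liver disease, diabetes mellitus, hypertension or heart disease" and admits such subjects provided their treatment has been stable for three months before Screening.

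Laboratory tests are scheduled at Screening and at Visit 7 (or early discontinuation). At Visit 11 they are done only if needed.

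**The concern.** A table introduced as showing changes will be read as showing what happened on the new dosage form. If the criterion looks only at the level, a subject who entered beyond the limit and stayed there is indistinguishable from one who crossed it during treatment.

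In a parallel-group safety table a control arm would carry a similar share of entry conditions, and the comparison would absorb them. Here it cannot. Visit 7 is the randomization visit, so its laboratory result precedes double-blind dosing. The two laboratory PCS tables are also not split by Part, whereas the vital-sign PCS tables (14.3.4.1.3 and 14.3.4.1.4) are. The only reference for a later value is the subject's own Screening value, and the PCS count does not use it. The safety profile is one of the primary objectives, so a percentage that mixes old and new abnormality matters for how that objective is reported.

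**Working it through.** The plan gives no expected PCS rate, so there is no figure to reproduce. The check is of definitions, followed by an illustration on assumed rates.

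**Step 1: how each safety measure treats entry status.**

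- Laboratory PCS (SAP 6.3.2): 10 hematology and 13 chemistry parameters; 0 of 23 have a Screening or change condition.
- Vital-sign PCS (SAP 6.3.3): 3 of 3 parameters require a level and a change from baseline.
- QTc (SAP 6.3.4): categories for the maximum value, with separate categories for the increase from Visit 2.
- TEAEs (SAP 6.3.1): the event must be new, or increased in severity or attribution.

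The laboratory PCS summary is the exception, and no reason is given.

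**Step 2: a case that the visible text allows.** A subject with treated diabetes enters under criterion 8 with random glucose of 190 mg/dL and has 190 mg/dL at Visit 7. The change is 190 − 190 = 0. The value exceeds the upper glucose limit of 180 mg/dL, so the subject meets the criterion.

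**Step 3: do other planned outputs show new cases?**

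- Shift tables (Protocol 10.4.5.4; SAP Tables 14.3.4.2.2 and 14.3.4.3.2) use the laboratory normal range. A value above normal at both visits shows no shift, whether or not it crossed the PCS limit in between.
- Change-from-Screening statistics describe the group and do not identify individuals.
- Listings with PCS flags allow a reader to reconstruct new cases by hand, but they give no summary.

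**Step 4: illustration for one parameter.** Let N be the subjects with a later value, q the share beyond the limit at Screening, p the share of those still beyond it later, and i the incidence among the rest. All of q, p and i are assumptions: q = 2% to 10%, p = 50% to 80%, i = 1% to 2%.

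- Count as written = N·q·p + N·(1 − q)·i
- New cases = N·(1 − q)·i
- Share from entry conditions = q·p / [q·p + (1 − q)·i]

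Results:

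- Lowest percentage as written: 0.02 × 0.5 + 0.98 × 0.01 = 0.0198, or 2.0%.
- Highest percentage as written: 0.10 × 0.8 + 0.90 × 0.02 = 0.098, or 9.8%.
- New cases among those at risk: 1% to 2% by assumption.
- Smallest entry share: 0.02 × 0.5 / (0.010 + 0.98 × 0.02) = 0.010 / 0.0296 = 34%.
- Largest entry share: 0.10 × 0.8 / (0.080 + 0.90 × 0.01) = 0.080 / 0.089 = 90%.

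With N = 300 (planned enrolment) the as-written count is about 6 to 29 and the new cases about 3 to 6. With N = 240 (planned minimum randomized) they are about 5 to 24 (240 × 0.0198 = 4.8; 240 × 0.098 = 23.5) and 2 to 5 (240 × 0.90 × 0.01 = 2.2; 240 × 0.98 × 0.02 = 4.7). The percentages do not depend on N.

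If Screening values themselves count, which the SAP does not exclude, p is in effect 1 and the as-written range becomes 3.0% (0.02 + 0.0098) to 11.8% (0.10 + 0.018). If q = 0, the two counts coincide and the effect is zero.

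**The case against.** The best reply is that the SAP never calls these results treatment-emergent. Its limit tables are headed as PCS values, the outputs are titled as PCS results, and the layout is left to table shells that are not in the documents. Laboratory results are otherwise summarized by visit. If the PCS tables follow that pattern, entry cases will sit in a Screening column. On this view, replacing one word in SAP 6.3.2 would settle the matter. The error also runs toward overstating abnormality, and the flagged listing holds every subject's Screening value.

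Much of this stands. A reader might infer that entry conditions are certain to be reported as on-treatment findings. The text does not support that, because the visits and layout are unspecified; it supports only that they can be.

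What does not stand is that a by-visit layout would be enough. Two marginal counts, at Screening and at Visit 7, do not show which Visit 7 subjects are new, and correcting the word would leave that gap.

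A fair warning also applies to the remedy. Simply excluding subjects already beyond a limit would hide further worsening, such as ALT rising from 3.2 to 9 times ULN.

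**Conclusion.** The point holds as a safety-reporting weakness. The mismatch between the description and the limits is definite, and so is the contrast with the vital-sign criteria. The route by which entry conditions can reach the tables rests on visible text about diabetes and liver disease. The size is unknown: it depends on case mix and on which visits are counted, and it may be zero. The 34% to 90% range is an illustration on assumed rates and not an estimate for this trial. The efficacy analyses and the randomized comparison are untouched.

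A reader might go further and infer that subjects with reduced renal function are admitted and will inflate the creatinine clearance row. The baseline list in Protocol 10.4.1 includes "Renal function (as estimated by calculated creatinine clearance", and SAP 6.3.1 plans TEAE summaries by "race, and renal impairment category". These show that renal function will be described. They do not show that subjects below the 70 mL/min limit may enter: no visible eligibility criterion addresses renal function, several numbered criteria are not visible in the public text, and the cut-offs of the renal categories are not visible either. No number of such subjects can be derived.

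**What to change.** In SAP 6.3.2 and in Tables 14.3.4.2.3 and 14.3.4.3.3:

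- State which visits count toward the PCS summary, and whether Screening, early-discontinuation and as-needed Visit 11 values are included.
- Cross-tabulate PCS status at Screening by PCS status after Screening for each parameter.
- Report newly met criteria, with subjects not meeting the limit at Screening and having a later value as the denominator.
- Keep subjects already meeting the limit at Screening in a separate row with their change from Screening, so that further worsening remains visible.
- Keep all flags in the by-subject listing, and describe the limits as values where no change is required.

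The cost is a few lines of SAP text and slightly more table programming. No new data are needed. The change should be made before unblinding.

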#### PCS Hematology Values:

Parameter	PCS values	
	S.I. Units	Conventional Units
White blood cells (WBC)	$\leq 2.8 \text{ or } \geq 16 \times 10^9/L$	$\leq 2.8 \text{ or } \geq 16 \times 10^9/L$
Lymphocytes	$\leq 0.5 \text{ or } \geq 4.5 \times 10^9/L$	$\leq 0.5 \text{ or } \geq 4.5 \times 10^9/L$
Monocytes	$\geq 1.5 \times 10^9 / L$	≥ 1.5 × 10  /L
Neutrophils	$\leq 1.0 \times 10^9/L$	$\leq 1.0 \times 10^{9}/L$
Eosinophils	$\geq 0.7 \times 10^9 / L$	$\geq 0.7 \times 10^{9}/L$
Basophils	$\geq 0.4 \times 10^9 / L$	$\geq 0.4 \times 10^{9}/L$
Red blood cells (RBC)	M: ≤ 2.5 × 10  /L F: ≤ 2.0 × 10  /L	M: ≤ 2.5 ×10°/mm³ F: ≤ 2.0 ×10°/mm³
Hemoglobin	M: ≤115 g/L F: ≤95 g/L	M: ≤ 11.5 g/dL F: ≤ 9.5 g/dL
Hematocit	M: ≤ 0.37 F: ≤ 0.32	M: ≤37% F: ≤32%
Platelet count	$\leq 75 \text{ or } \geq 700 \times 10^9/L$	$\leq 75 \text{ or } \geq 700 \times 10^9 / \text{L}$

S.I. = International System of Units

#### **PCS Blood Chemistry Parameters**

Parameter	PCS values	
	S.I. Units	Conventional Units
Sodium	≤ 115 or ≥ 155 mmol/L	≤ 115 or ≥ 155 mEq/L
Potassium	≤ 3.0 or ≥ 5.8 mmol/L	$\leq$ 3.0 or $\geq$ 5.8 mEq/L
Glucose (random)	≤ 2.775 or ≥ 9.99 mmol/L	≤ 50 or ≥ 180 mg/dL
BUN	≥ 30 mg/dL	> 30 mg/dL
Creatinine	≥ 176.8 µmol/L	≥ 2.0 mg/dL
Calcium, plasma	≤ 1.75 or ≥ 3.875 mmol/L	≤ 7 or ≥ 15.5 mg/dL
ALT / SGPT	≥ 3 × ULN	≥ 3 × ULN
AST / SGOT	≥ 3 × ULN	≥ 3 × ULN
Alkaline phosphatase (ALK-P)	≥ 3 ×ULN	≥ 3 × ULN
Total bilirubin	≥ 34.2 µmol/L	≥ 2.0 mg/dL
Total protein	≤ 45 or ≥ 90 g/L	$\leq 4.5 \text{ or } \geq 9.0 \text{ g/dL}$
Albumin	≤ 25 or ≥ 65 g/L	$\leq 2.5 \text{ or } \geq 6.5 \text{ g/dL}$
Creatinine clearance	< 70 mL/min	< 70 mL/min

S.I. = International System of Units; ULN = upper limit of the [normal] reference range Medium = serum, unless otherwise noted

Clinical laboratory results will be listed for all subjects, inclusive of flags for whether or not the value is outside laboratory normal range, considered significant by the Investigator, or meet the pre-specified criteria for being possibly clinically significant. Normal ranges will be noted in the listing. Values outside laboratory normal ranges as well as those considered clinically significant by the Investigator will be flagged as L (low) and H (high).

# 6.3.3 Vital Signs

Sitting diastolic and systolic blood pressures, resting pulse measurements, respiration, and body temperature (°C) at each visit will be summarized using descriptive statistics (n, mean, 95% confidence interval, standard deviation, median, minimum, and maximum) for measurements during the open-label phase and also by treatment groups during the randomized double-blind withdrawal phase. Similarly, change from Visit 1 at each visit will be summarized using descriptive statistics. For the summary of change statistics, the Baseline mean and standard deviation will be provided for the subset of subjects with available data for the change summary. Appropriate visit windows for categorizing results will be established prior to database lock and unblinding.

For summary purposes, if more than one vital sign measurement is available for an analysis visit, then the latest value of each parameter will be used.

Values considered possibly clinically significant by the Investigator are to be flagged. Criteria for possibly significant changes are presented in the table below. Number and percentages of subjects with values of clinical significance will be summarized for each study Part; in Part 3, summaries will be by treatment group.

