#### 6.3.4 12-Lead ECG

Electrocardiograms will be performed at Screening, Visits 2, 4, 7, and 11. Only one assessment will be made at Screening, while assessments will be made in triplicate at later visits. All triplicate results will be averaged for summary and analysis purposes. Parameters to be summarized include: HR, PR, RR, QRS, QT, and QTc. The QTc interval will be presented by both the Bazett (QTcB = QT/(RR)1/2) and the Fridericia (QTcF = QT/(RR)1/3) corrections. For QTcF and QTcB at each study visit, the distribution of maximum values ( $\leq$  450, >450 -  $\leq$  480, >450 males, >470 females, >480 -  $\leq$  500, and >500 msec) as well as the distribution of the greatest change from Visit 2 (0 or less [no increase], 1-29 msec, 30-60 msec, > 60 msec, and >60 msec increase or >500 msec) will be presented. Appropriate visit windows for categorizing results will be established prior to database lock and unblinding.

When more than one value is available within a given visit window, the latest value will be used for tabulation purposes.

ECG results will be summarized by treatment group and visit. Descriptive statistics will include mean, 95% confidence interval, standard deviation, median, minimum, and maximum. Continuous ECG parameters will be summarized as change from Baseline (Visit 2). For the summary of change statistics, the Baseline mean and standard deviation will be provided for the subset of subjects with available data for the change summary. Clinical interpretations will also be summarized by visit and treatment group. Any ECG abnormalities, based on clinical interpretation, will be listed.

ECG results, including clinical interpretation and a flag for whether or not the value meets criteria for being possibly clinically significant, will be listed for all subjects.

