Table 14.3.1.2.7	Incidence of Treatment-Emergent Adverse Events Leading to Discontinuation by Treatment Group in Part 3 (Safety Population)	
Table 14.3.1.2.8	Incidence of Treatment-Emergent Adverse Events by Gender by Treatment Group in Part 3 (Safety Population)	
Table 14.3.1.2.9	Incidence of Treatment-Emergent Adverse Events by Age Group by Treatment Group in Part 3 (Safety Population)	
Table 14.3.1.2.10	Incidence of Treatment-Emergent Adverse Events by Race by Treatment Group in Part 3 (Safety Population)	
Table 14.3.1.2.11	Incidence of Treatment-Emergent Adverse Events by Concomitant Medications in at Least 20% of Subjects by Treatment Group in Part 3 (Safety Population)	
Table 14.3.1.2.12	Incidence of Treatment-Emergent Adverse Events by Medical Conditions Present in at Least 20% of Subjects at Screening by Treatment Group in Part 3 (Safety Population)	
Table 14.3.1.2.13	Incidence of Treatment-Emergent Adverse Events by Renal function by Treatment Group in Part 3 (Safety Population)	
Table 14.3.1.2.14	Incidence of Treatment-Emergent Adverse Events by Dose at Earliest Onset by Treatment Group in Part 3 (Safety Population)	
Table 14.3.2.1.1	Incidence of Treatment-Emergent Serious Adverse Events in Part 2 (Safety Population)	
Table 14.3.2.1.2	Incidence of Treatment-Related Treatment-Emergent Serious Adverse Events by Highest Relationship in Part 2 (Safety Population)	
Table 14.3.2.1.3	Incidence of Fatal Treatment-Emergent Serious Adverse Events in Part 2 (Safety Population)	
Table 14.3.2.2.1	Incidence of Treatment Emergent Serious Adverse Events by Treatment Group in Part 3 (Safety Population)	
Table 14.3.2.2.2	Incidence of Treatment-Related Treatment-Emergent Serious Adverse Events by Highest Relationship in Part 3 (Safety Population)	
Table 14.3.2.2.3	Incidence of Fatal Treatment-Emergent Serious Adverse Events in Part 3 (Safety Population)	
Table 14.3.4.1.1	Vital Signs in Part 2 (Safety Population)	
Table 14.3.4.1.2	Vital Signs in Part 3 (Safety Population)	
Table 14.3.4.1.3	Potentially Clinically Significant Vital Signs in Part 2 (Safety Population)	
Table 14.3.4.1.4	Potentially Clinically Significant Vital Signs in Part 3 (Safety Population)	
Table 14.3.4.2.1	Hematology Laboratory Assessments (Safety Population)	
Table 14.3.4.2.2	Hematology Laboratory Shift Table (Safety Population)	
Table 14.3.4.2.3	Number and Percentage of Subjects with a Possibly Clinically Significant (PCS) Hematology Results – Safety Population	

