Table 14.3.4.3.1	Chemistry Laboratory Assessments (Safety Population)	
Table 14.3.4.3.2	Chemistry Laboratory Shift Table (Safety Population)  Number and Percentage of Subjects with a Possibly Clinically Significant (PCS)	
Table 14.3.4.3.3	Chemistry Results – Safety Population	
Table 14.3.4.4	Urinalysis Summary (Safety Population)	
Table 14.3.4.5.1	12-Lead Electrocardiogram Parameters in Part 2 (Safety Population)	
Table 14.3.4.5.2	12-Lead Electrocardiogram Parameters in Part 3 (Safety Population)	
Table 14.3.4.5.3	Clinical Interpretation and Categorical Results of 12-Lead Electrocardiogram in Part 2 (Safety Population)	
Table 14.3.4.5.4	Clinical Interpretation and Categorical Results of 12-Lead Electrocardiogram in Part 3 (Safety Population)	

Version 9.0

	C-SSRS Summary of Suicidal Ideation and Suicidal Behavior in Part 1 (Safety
Table 14.3.5.1	Population)
	C-SSRS Summary of Suicidal Ideation and Suicidal Behavior in Part 2 (Safety
Table 14.3.5.2	Population)
	C-SSRS Summary of Suicidal Ideation and Suicidal Behavior in Part 3 (Safety
Table 14.3.5.3	Population)

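### Part 3 by-arm change summaries use Visit 1 (vital signs) or Visit 2 (ECG) as reference; the available text plans no within-subject change from randomisation at Visit 7

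*SAP*

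**What the plan says.** **Vital signs.** SAP 6.3.3 summarises values at each visit for the open-label phase and "also by treatment groups during the randomized double-blind withdrawal phase". The next sentence sets the reference for change: "Similarly, change from Visit 1 at each visit will be summarized using descriptive statistics". Protocol 10.4.5.3 gives the same rule.

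**ECG.** Under SAP 6.3.4, "ECG results will be summarized by treatment group and visit". The reference for change is stated twice. For the continuous parameters, "Continuous ECG parameters will be summarized as change from Baseline (Visit 2"). For QTcF and QTcB, the categories describe "the distribution of the greatest change from Visit 2".

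**Tables.** SAP 9.1 lists separate Part 3 tables for vital signs (14.3.4.1.2), ECG parameters (14.3.4.5.2) and ECG categorical results (14.3.4.5.4).

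**Baseline in general.** SAP 4.6 leaves the baseline of each assessment to its own section. Neither 6.3.3 nor 6.3.4 mentions change from Visit 7, the visit at which SAP 3.2.2 places randomisation.

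**Visit 11 ECG.** SAP 6.3.4 lists Visit 11 among the ECG visits without a condition. SAP 3.2, protocol Table 1 and the protocol's final-visit list make that ECG conditional on need.

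**The concern.** SAP 3.1.1 sets the primary objectives as a comparison of continued treatment with down-titration to placebo, and the safety profile is one of them. In a randomised withdrawal phase, a natural safety question is what changed in each arm after Visit 7. Change measured from Visit 1 or Visit 2 answers a different question: what has changed since the study, or the new formulation, began. That cumulative view is legitimate. It mixes about 16 to 17 weeks of open-label time, common to both arms, with at most four weeks of randomised time.

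The plan does move the reference point to Part 3 elsewhere. Protocol 10.4.5.1 judges emergence of Part 3 adverse events against the double-blind medication. SAP 5.1 redefines the safety population for Part 3. SAP 6.1.7 re-checks concomitant status for Part 3. The visible vital-sign and ECG text has no such step and gives no reason for its absence.

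At stake is how readable the descriptive safety tables are, not the validity of any test.

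**Working it through.** There is no planned figure to reproduce. The check is day arithmetic, followed by what each reference can and cannot show.

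**1. Share of the change interval before randomisation.** Study days from the schema (SAP Table 1; same in protocol 4.1): Visit 1 = 1, Visit 2 = 8, Visit 7 = 120, Visits 8 to 11 = 127, 134, 141, 148.

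Share = (day of Visit 7 − day of reference) / (day of visit − day of reference).

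| Measure | Visit | Share before randomisation | Days after Visit 7 |
|---|---|---|---|
| Vital signs, from Visit 1 | 8 | 119/126 = 94.4% | 7 |
| | 9 | 119/133 = 89.5% | 14 |
| | 10 | 119/140 = 85.0% | 21 |
| | 11 | 119/147 = 81.0% | 28 |
| ECG, from Visit 2 | 11 | 112/140 = 80.0% | 28 |

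The ±1-day windows on Visits 7 to 10 (protocol 4.4.4.1 to 4.4.4.4), with Visit 1 fixed, move this little:
- Visit 8: 118/127 = 92.9% to 120/125 = 96.0%
- Visit 9: 118/134 = 88.1% to 120/132 = 90.9%
- Visit 10: 118/141 = 83.7% to 120/139 = 86.3%

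These are calendar shares. They do not measure bias or precision. With Visit 7 as reference the share is zero.

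**2. Is the between-arm difference biased?** For each subject, (Visit 11 − Visit 1) = (Visit 11 − Visit 7) + (Visit 7 − Visit 1). The last term is complete before allocation, so its expected difference between arms is zero. The reference visit introduces no bias.

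**3. Can change since Visit 7 be recovered from the planned levels?** Subtracting group means gives the mean change only if the same subjects contribute at both visits. The SD of change needs the correlation r between Visit 7 and the later visit, because Var(change) = s₇² + s₁₁² − 2·r·s₇·s₁₁, and no planned summary reports r. SAP 6.3.3 and 6.3.4 give matched-subset means and SDs for the baseline visit only.

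**4. What the QTc categories show.** Four hypothetical subjects, in msec:

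| Subject | Visit 2 to 7 | Visit 7 to 11 | From Visit 2: change, category | From Visit 7: change, category |
|---|---|---|---|---|
| A | +35 | 0 | +35, 30-60 | 0, 0 or less |
| B | +35 | −35 | 0, 0 or less | −35, 0 or less |
| C | 0 | +35 | +35, 30-60 | +35, 30-60 |
| D | 0 | 0 | 0, 0 or less | 0, 0 or less |

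The planned Visit 2 categories separate A from B. They do not separate A from C (rise before or after randomisation) or B from D (reversal or no change at all). The same categories taken from Visit 7 would separate A from C but put A, B and D together. Continuous change from Visit 7 separates A from C and B from D.

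**5. Illustration of size, on assumed values.** The documents give no QTc mean or SD. Assume normally distributed change with SD s, an open-label mean shift d and no true change after Visit 7. Then P(rise ≥ 30 from Visit 2) = 1 − Φ((30 − d)/s), and from Visit 7 it is 1 − Φ(30/s).

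- s = 15: 2.3% from Visit 7. From Visit 2: 2.3%, 4.8%, 9.1% and 15.9% for d = 0, 5, 10 and 15.
- d = 10, other SDs: 0.1% from Visit 7 and 2.3% from Visit 2 at s = 10; 6.7% and 15.9% at s = 20.

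With no open-label shift the two references agree. Any excess is equal between arms in expectation.

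**The case against.** Several points on the other side stand.

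- **The tables are not mislabelled.** A reader might infer that change before randomisation is passed off as Part 3 change. The SAP names Visit 1 and Visit 2 as the references, and Visit 7 levels should appear among the by-visit summaries. Listings 16.2.9 and 16.2.10 would let someone derive individual changes by hand.
- **No bias, and no demonstrated loss of precision.** A reader might also infer that the randomised safety comparison is distorted. Step 2 shows that it is not. Any effect on precision depends on correlations between visits that the documents do not give.
- **Visit 7 QTc categories alone would be worse in one respect.** As step 4 shows, the present list puts every fall in its lowest class, so a reversal on withdrawal would vanish. This limits the remedy.
- **Part of the text is unavailable.** The table shells are not in the documents. The protocol section between 10.4.5.4 and 10.4.5.6 is absent, as is the footnote to the starred baseline in the vital-sign criteria of SAP 6.3.3. The schedule in SAP Table 2 carries a baseline label whose column cannot be placed. A Visit 7 summary may exist in one of these, and nothing can be concluded about the vital-sign threshold counts.
- **The adverse-event rule is only an analogy.** It classifies events and does not oblige continuous measures to follow.

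These points narrow the concern but do not remove it. A table titled for Part 3 can properly carry a cumulative reference, but it should also show change over Part 3, and listings are not a summary.

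**Conclusion.** The concern holds in a limited form. In the available text, Part 3 change by arm is referenced only to Visit 1 or Visit 2, so 81% to 94% of the vital-sign interval and 80% of the ECG interval at Visit 11 fall before randomisation. Within-subject change since Visit 7 is not planned and cannot be rebuilt from the group summaries. The documents do not support a claim of mislabelling, bias or lost precision, and efficacy is not touched. The QTc percentages in the working are illustrations on assumed values and do not show that an open-label shift occurs in this trial.

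The wording conflict on the Visit 11 ECG is separate, and a new reference visit would not resolve it. Visit 11 is the only ECG visit scheduled after randomisation. If it is done only when needed, Part 3 ECG change rests on a selected subset whichever reference is used.

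Confidence is moderate because of the missing text. This is a worthwhile, low-cost improvement to descriptive tables; the main conclusions do not depend on it.

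**What to change.** 1. Add continuous change from Visit 7, by arm, to the Part 3 vital-sign and ECG tables. Include the Visit 7 mean and SD for the subjects who contribute to each change.
2. Keep the Visit 1 and Visit 2 summaries, including the QTc categories, as the cumulative view. State the reference visit in each table title or column heading.
3. Add QTc-change categories from Visit 7 only if categories for decreases are added too.
4. Reconcile SAP 6.3.4 with SAP 3.2 and the protocol on whether the Visit 11 ECG is routine or conditional. If it is conditional, give by-arm denominators and label the Part 3 ECG results as a selected subset.

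**Cost.** One further baseline flag and a few tables. Vital signs and triplicate ECGs are already scheduled at Visit 7, so no new data are needed. A Visit 7 reference used alone would hide any shift acquired in Part 2, which is why the cumulative view stays. The ECG gain is limited to subjects who have a Visit 11 ECG.
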